3. SUBJECT POPULATIONS

3.1. Population Definitions

The following analysis sets will be evaluated and used for presentation and analysis of the data:

- Pilot Phase Safety: All patients exposed to at least 1 dose of IMP during the pilot phase will be used for summaries of the safety endpoints during the pilot phase.
- OLE Phase Safety: All patients exposed to at least 1 dose of IMP during the OLE phase will be used for summaries of the safety endpoints during the OLE phase.

3.2. Protocol Deviations

All protocol deviations will be listed and reasons for exclusion from the analysis sets will be summarized.

4. STATISTICAL METHODS

4.1. Sample Size Justification

The pilot phase of the study is not powered and comprises of 9 patients.

4.2. General Statistical Methods and Data Handling

4.2.1. General methods

All output will be incorporated into Microsoft Word files, sorted and labeled according to the International Conference on Harmonisation (ICH) recommendations, and formatted to the appropriate page size(s).

Tabulations will be produced for appropriate demographic, baseline, and safety parameters. For categorical variables, summary tabulations of the number and percentage within each category (with a category for missing data) of the parameter will be presented. For continuous variables, the mean, median, standard deviation, minimum and maximum values will be presented.

Given that only the pilot and OLE phases will be analyzed in this study, there will be no formal hypothesis testing. Descriptive statistics will be used in the analyses. Data from the pilot and OLE phases will be presented together in the same outputs, unless otherwise noted. All tabulations will display one treatment column since the pilot and OLE phases only consist of one open-label treatment group.

4.2.2. Computing Environment

All descriptive statistical analyses will be performed using SAS statistical software (Version 9.4 or higher), unless otherwise noted. Medical History and adverse events will be coded using Medical Dictionary for Regulatory Activities (MedDRA) version 19.0. Concomitant medications will be coded using World Health Organization Drug Dictionary (WHO-DD, Q2.2016).

4.2.3. Methods of Pooling Data

Not applicable to the present study.

4.2.4. Adjustments for Covariates and Stratification

No formal statistical analysis that adjusts for possible covariate effects is planned.

4.2.5. Multiple Comparisons/Multiplicity

Multiplicity is not of concern for this study with a descriptive interpretation.

4.2.6. Subpopulations

No analyses of subgroups of subjects are planned.

4.2.7. Withdrawals, Dropouts, Loss to Follow-up

Subjects who withdraw from the study will not be replaced.

4.2.8. Missing, Unused, and Spurious Data

In general, there will be no substitutions made to accommodate missing data points. All data recorded on the CRF will be included in data listings that will accompany the clinical study report.

4.2.8.1. Adverse Events Onset Date

In the case an AE onset date is missing or partially missing, an imputation needs to be done to determine if the event is to be classified as occurring during the treatment period.

If an onset date is completely **missing** (or the year is missing), the **derived onset date** will be calculated as the first non-missing valid (actual) date from the following list (in order of precedence):

- First active study medication date
- Consent date
- If a valid non-missing date is not available for any of these dates, the derived onset date will be set to missing.

If an onset date is incomplete, the derived onset date will be calculated using the following algorithm:

Calculate a surrogate date as the first non-missing valid date from the following list (in order of precedence):

- First active study medication date
- Consent date
- If a valid non-missing date is not available for any of these dates, the surrogate date will be set to missing.

Based on the information provided, set the initial derived date to the earliest possible date. If only a year is provided, set the derived date to January first of that year. If a year and month is provided, set the derived date to the first day of that month.

If the surrogate date is non-missing then:

- If the derived date is on or after the surrogate date use the derived date as calculated
- If the derived date is prior to the surrogate date and the surrogate date is consistent with the partial data provided for the onset date, use the surrogate date as the derived date
- If the derived date is prior to the surrogate date and the surrogate date is not consistent with the partial data provided for the onset date then set the derived onset date to be the latest possible date based on the partial onset date information provided. If only a year is provided, set the derived date to December 31st of that year. If a year and month is provided, set the derived date to the last day of that month.

If all dates used to determine the surrogate date are missing, then based on the information provided, set the derived date to the earliest possible date. If only a year is provided, set the derived date to January first of that year. If a year and month is provided, set the derived date to the first day of that month.

4.2.8.2. Adverse Events End Date

A missing or incomplete end date of an AE will be imputed according to the following conventions:

- If an end date is missing, the derived end date will be set to missing
- If an end date is incomplete, set the derived end date to be the latest possible date based on the partial onset date information provided. If only a year is provided, set the derived date to December 31st of that year. If a year and month is provided, set the derived date to the last day of that month.

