12.4 Causality Assessment

Causality assessment is required for all AEs and SAEs. Causality assessment must only be assigned by the investigator. All cases judged as having a reasonable suspected causal relationship to the IMP must be reported as such. The expression "reasonable causal relationship" is meant to convey in general that there are facts (evidence) or arguments to suggest a causal relationship.

The following question which must be answered by the investigator for all AEs is used to capture the reasonable causal relationship of an event to the IMP:

"In your opinion is there a plausible relationship to the IMP?" The answer is either "yes" or "no".

Events that start before the first dose of IMP (pre-treatment) should be considered as not causally related. Where a pre-treatment event worsens in severity following the first dose of IMP, a new event record should be entered into the CRF.

Considering the explanation given above, investigators are strongly encouraged to express their opinion on what the cause of an AE might be. For individual patients, the investigator is usually in the best position to assess the underlying suspected cause of an AE. For all AEs and especially SAEs, it is important that the investigator assess not only the possible role of the IMP but also other potential contributing factors. Factors for consideration of the underlying cause may include:

- Medical and disease history.
- Lack of efficacy/worsening of treated condition.
- Concomitant or previous treatment.
- Withdrawal of IMP.
- Protocol-related procedure.

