4.2.8.3. Adverse Events Severity and Relationship

The missing AE severity will be imputed to be "severe" and the missing AE relationship to study drug will be imputed to be "definitely related".

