4.8.2. Adverse Events

Adverse events will be coded using the latest version of MedDRA and displayed in tables and listings using SOC and PT.

Analyses of AEs will be performed for those events that are considered treatment emergent AEs (TEAEs), where treatment emergent is defined as any adverse event that started, or worsened in severity or seriousness, following the first dose of IMP.

The number and percentage of subjects with the following AEs will be summarized:

- All-causality TEAEs
- Treatment-related TEAEs

- All-causality TEAEs by severity
- All-causality TEAEs by sex
- All-causality non-serious TEAEs
- All-causality serious TEAEs
- Treatment-related serious TEAEs
- TEAEs reported as leading to permanent cessation of study treatment
- Treatment-related TEAEs reported as leading to permanent cessation of study treatment
- Fatal TEAEs.

In these tabulations, each subject will contribute only once (i.e., the most related occurrence or the most intense occurrence) to each of the incidence rates in the descriptive analysis, regardless of the number of episodes. No formal hypothesis-testing analysis of adverse events incidence rates will be performed.

All adverse events occurring on study will be listed by cohort and subject. Listings will also be provided for the following: subject deaths; SAEs; and adverse events leading to withdrawal of study drug.

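### The SAP's AE onset rule defaults to pilot Day 1 without checking the recorded end date or OLE entry, so undated events can be misclassified; two other AE imputation rules are miswritten.

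*SAP*

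**What the plan says.** **Onset (SAP 4.2.8.1).** If the whole date or the year is absent, the derived onset "will be calculated as the first non-missing valid (actual) date from the following list (in order of precedence"). The list holds first active study medication, then consent. A partial onset starts at its earliest possible date. If that precedes the first dose and the first dose fits the recorded part, the first dose is used. If the first dose does not fit, the instruction is "then set the derived onset date to be the latest possible date based on the partial onset date information provided". The stated purpose is to decide whether the event belongs to the treatment period. The end date and OLE entry are not mentioned.

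**End (SAP 4.2.8.2).** For an absent date: "If an end date is missing, the derived end date will be set to missing". For an incomplete one: "set the derived end date to be the latest possible date based on the partial onset date information provided".

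**Relationship (SAP 4.2.8.3).** The SAP states that "the missing AE relationship to study drug will be imputed to be" *definitely related*. Protocol 12.4 collects causality with one question, "In your opinion is there a plausible relationship to the IMP", answered yes or no.

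**Where the values are used.** SAP 2.2 has every patient start GWP42003-P in the pilot and carry it into the OLE. SAP 6.1 plans separate pilot and OLE AE tables, as Protocol 13.6.5.2 requires.

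**Dictionary.** SAP 4.2.2 has events "coded using Medical Dictionary for Regulatory Activities (MedDRA) version 19.0". SAP 4.8.2 says "Adverse events will be coded using the latest version of MedDRA".

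**The concern.** The onset rule answers one question, whether the event was on treatment, but the tables need a second answer: which phase. Defaulting to the first dose is a conservative answer to the first question. It carries no information on the second, because all infants share the same anchor, pilot Day 1.

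Even for the first question, the rule ignores information that may settle it. AEs are collected from screening, so an event can start and stop before dosing. If its onset is undated, the rule makes it treatment-emergent whatever its recorded end date. Protocol 12.4 treats events that start before the first dose as not causally related.

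Safety is a primary endpoint of the pilot and the primary endpoint of the OLE (SAP 2.5), and the phase-specific AE tables are its main display.

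The end-date and relationship rules are a different kind of problem: their wording cannot be carried out as it stands in every case, so the programmer must guess the intent.

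**Working it through.** There is no plan figure to reproduce. The rules were applied to assumed calendar dates.

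**1. Undated OLE event.** Assume Day 1 = 6 Feb 2017 and true onset on Day 200 = 24 Aug 2017.
- No date or no year recorded: derived onset 6 Feb 2017 (Day 1).
- Year only (2017): earliest date 1 Jan 2017 is before Day 1, and Day 1 fits 2017, so derived onset is 6 Feb 2017.
- Month and year (Aug 2017): derived onset 1 Aug 2017, correctly in the OLE.

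**2. Share of OLE events placed in the pilot.** Day 1 was set to each day of a 365-day year and true onset to each of Days 16 to 379. An event counted as pilot if its derived onset was Day 15 or earlier.

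| Onset information recorded | Range over Day 1 dates | Mean |
|---|---|---|
| None, or no year | 100% throughout | 100% |
| Year only | 0% to 100% | 50% |
| Month and year | 0% to 8% | 4% |

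The year-only range depends on how much of the OLE lies in the first-dose calendar year. These shares are conditional on an onset being incomplete. They also weight all OLE days equally.

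**3. Event that ended before dosing.** Keep Day 1 = 6 Feb 2017, with onset undated and end recorded as 3 Feb 2017. The derived onset is 6 Feb 2017, which is 6 − 3 = 3 days after the event ended, and the event counts as treatment-emergent. If onset were required to be no later than the end, it would be 3 Feb or earlier and the event would be pre-treatment.

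**4. Weight of one subject.** SAP 4.1 gives 9 pilot patients: 1/9 = 11%.

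**5. End date.** Take onset recorded as Dec 2017 and end as Jan 2018. Completed from onset information, the end is 31 Dec 2017, before the earliest date the record allows (1 Jan 2018). Completed from its own parts, it is 31 Jan 2018. If onset is complete, there is no partial onset information and the rule is undefined. If a programmer nevertheless used the onset month, the derived end would precede the true end for 10%, 23%, 46% and 98% of start days for events lasting 3, 7, 14 and 30 days.

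**6. Relationship.** The collected values are yes and no; the imputed value is neither, and no mapping is stated. SAP 4.8.2 likewise counts each subject's most related occurrence, which presumes a graded scale. The severity imputation is sound: severe is one of the three grades in Protocol 12.5.

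**The case against.** The case for leaving the text alone is fair in several respects.

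- **Rarity.** Protocol 12.5 does not normally accept missing or partial dates, asks for an estimate when the exact date is unknown, and expects month and year or, exceptionally, the year alone. Protocol 12.4 requires the causality question to be answered for every AE. This stands: few records should be affected, and the number is unknown.
- **Convention.** First-dose anchoring is a usual conservative choice for treatment emergence. This stands where nothing else is known. It does not cover an event whose recorded end precedes the first dose, or the choice of phase.
- **Phase assignment.** The SAP never says that phase follows the derived onset. That is correct, so the misplacement is conditional. The SAP offers no other rule.
- **Evident intent.** The end-date phrase repeats the onset rule's wording and looks carried over; the sentences after it could be programmed from the end date's own parts. *Definitely related* plainly means related. Both points stand.
- **No inference at risk.** The analyses are descriptive and the recorded data go into listings (SAP 4.2.1, 4.2.8), so a careful reader could spot an anomaly. This lowers the stakes but does not make the tabulated counts right.

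**Conclusion.** The onset rule is wrong as written in two ways. Followed exactly, it can make an event that ended before dosing treatment-emergent. If phase is taken from the derived onset, it also places every wholly undated OLE event, and a date-dependent share of year-only ones, in the pilot tables. The effect is confined to a few records, each worth up to 11 percentage points of a nine-infant cell. The end-date and relationship rules need correcting, but with little or no effect on the planned tables if programmed as intended. The MedDRA mismatch is clerical.

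Stronger conclusions that a reader might draw are not supported:
- *End dates will be wrong by months.* An onset of 12 March with an end of June might be read as giving 31 March, 91 days before 30 June. That onset is complete, so the rule is undefined and gives no definite date. No table in SAP 6.1 uses AE end date or duration.
- *Imputed related events will drop out of the treatment-related tables.* This requires a program that selects only on yes. No program or CRF is in the documents.
- *Most undated events must belong to the OLE because the pilot is 14 of 378 days (14/378 = 3.7%).* This assumes events spread evenly over time in an infant who completes the OLE. The documents support neither assumption.

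**What to change.** 1. **SAP 4.2.8.1.** Require the derived onset to be no later than the recorded end date or, if that is incomplete, its latest possible value. An event that ended before the first dose is then not treatment-emergent. Where other recorded information (for example the caregiver diary in Protocol 9.2.13) shows that the event began in the OLE, anchor it to the first OLE dose. OLE dosing already defines the OLE safety set in SAP 3.1. If the phase cannot be determined, keep the first-dose default and footnote the event. State that phase is assigned from the resulting date.
2. **SAP 4.2.8.2.** Replace *onset* with *end*, and cap the derived end at last contact.
3. **SAP 4.2.8.3.** Impute a missing relationship as *yes*.
4. **Clerical.** Name one MedDRA version in 4.2.2 and 4.8.2.

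An event of unknown phase should not be counted in both phase tables: that would enter it in a phase where it did not occur. Nor should the rule rely on the visit of first report, which is not among the AE fields in Protocol 12.5.

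The cost is a few sentences of SAP text, minor programming and a few footnoted events. Data collection does not change.

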4.2.8.3. Adverse Events Severity and Relationship

The missing AE severity will be imputed to be "severe" and the missing AE relationship to study drug will be imputed to be "definitely related".

4.2.9. Baseline Definition

Unless otherwise noted, baseline (for both the pilot and OLE phases) is defined as the data most recently collected prior to the first IMP dosing start date/time in the pilot phase. If the timing of some data collection is not recorded, it will be assumed that the assessment at the first dosing date is performed as planned, i.e. prior to dosing in the pilot phase.

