9.1.1.2 Visit 2 (Day 1 [+3 Days])

This visit will occur up to 7 (+3) days after Visit 1 (screening). Patients who satisfy all eligibility criteria (Section 6) during the screening period will be assigned GWP42003-P (pilot phase) or randomly allocated to GWP42003-P or matching placebo (pivotal phase) using the IVRS/IWRS (Section 9.2.2). Eligible patients must begin treatment within 7 days of their video-EEG screening assessment. The following will be collected/assessed prior to the patient receiving IMP:

- Concomitant medication review (Section 9.2.5).
- Physical examination (Section 9.2.6).
- Vital signs (Section 9.2.7).
- CGIC memory aid (Section 9.2.12.1).
- PGIC memory aid (Section 9.2.12.2).
- Vineland-II (Section 9.2.12.3).
- Caregiver diary review (Section 9.2.13) for:
 - Spasm/seizure information.
 - Changes in concomitant AEDs.
 - Usage of rescue medication.
 - AEs.
- AEs (Section 12).

Patients will receive sufficient IMP for 2 weeks of dosing. Patients in the pilot phase will remain in the clinic as inpatients during the 4-day titration period. For all patients, the first dose of IMP will be taken in the clinic on the morning of Day 1 with

EudraCT Number: 2015-004904-50

Protocol V3 20Sep16

an ECG assessment between 3 and 5 hours postdose (Section 9.2.8). For patients involved in the pivotal phase of the trial, a PK blood sample will be taken, provided the risk/benefit outcome is favorable in the investigator's opinion (Section 9.2.11). If a PK blood sample is collected, the investigator must note the sampling time and the dosing times of IMP and of any concomitant AEDs taken that day and the previous day. Patients will titrate to their target dose of GWP42003-P (or equivalent volume of placebo in the pivotal phase; Section 8.1.2) and will continue at this dose, or the highest tolerated dose up to 40 mg/kg/day, for the remainder of the 2-week treatment phase. During this time, the patient's current IS therapy may be continued or tapered, at the discretion of the investigator. All non-pharmacological interventions for epilepsy (including ketogenic diet and any neurostimulation devices for epilepsy) must remain stable during the pilot and pivotal phases of the trial. Following Visit 2, daily safety checks will be made during the first week of IMP dosing.

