9.1.1.4 Visit 3 (Day 4 [+1 Day])

This visit will occur 3 (+1) days after Visit 2. The following will be collected/assessed:

- Concomitant medication review (Section 9.2.5).
- Vital signs (Section 9.2.7).
- ECG (prior to the day's first dose of IMP; Section 9.2.8).
- Clinical laboratory samples (blood and urine [if possible]; Section 9.2.10) for:
 - Serum biochemistry.

- Hematology.
- Urinalysis.
- Caregiver diary review (Section 9.2.13) for:
 - Spasm/seizure information.
 - IMP usage.
 - Changes in concomitant AEDs.
 - Usage of rescue medication.
 - AEs.
- AEs (Section 12).

All patients will take their IMP in the clinic with an additional ECG assessment between 3 and 5 hours postdose (Section 9.2.8). Patients in the pilot phase will then be discharged from the clinic.

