9.2.7 Vital Signs

Vital signs measurements (systolic and diastolic blood pressure, pulse rate, body temperature and respiratory rate), taken in a supine position at rest for 5 minutes, will be completed alongside the physical examination. The methods/procedures employed for vital signs measurements must be consistent throughout the trial, where possible. Any deviation in methods used must be reported to the study monitor.

9.2.8 12-lead Electrocardiogram

ECG recordings will be performed after 5 minutes in a supine position. A physician must review the ECG immediately (annotated, signed and dated) and any abnormal findings considered to indicate significant medical history or AEs must be recorded appropriately on the CRF. Additional ECG measurements can be taken at any time during the trial, if clinically indicated.

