⁴Safety follow-up visit is to occur 28 (+3) days after date of final dose (including tapered dose); weekly (±3 days) telephone calls must be made during the follow-up period. Each safety telephone call will conduct the same assessments as listed for safety follow-up visit.

⁵Based on assessment of clinical laboratory and video-EEG results.

 $^{^6\}mathrm{ECG}$ to be performed between 3 and 5 hours after the day's first dose of IMP only.

⁷ECG to be performed both prior to the day's first dose of IMP and between 3 and 5 hours after this dose.

⁸Only for patients involved in the pivotal phase, and progressing to the OLE from the pivotal phase. To be conducted only if the risk/benefit outcome is favorable, in the investigator's opinion.

⁹Memory aid only (worksheet completed).

¹⁰If necessary, IMP will also be dispensed for taper period.

¹¹IMP usage to be recorded on a dosing schedule which will form part of the paper diary

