4.2.10. Visit Windows

Any clinical domains that are displayed by visit will be shown by nominal study visit.

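### SAP 4.2.9 assumes an untimed first-dosing-date assessment was pre-dose, but the Day 1 ECG is planned post-dose only; the fallback should exclude ECG (minor)

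*SAP*

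**What the plan says.** SAP 4.2.9 defines one baseline for both the pilot and OLE phases: the most recent data before the first pilot-phase dose. For data without a recorded time, it adds that "it will be assumed that the assessment at the first dosing date is performed as planned, i.e. prior to dosing in the pilot phase". No type of assessment is excepted.

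The schedule treats the first-dosing-date ECG differently. Footnote 6 to SAP Table 1 has the Visit 2 ECG "to be performed between 3 and 5 hours after the day's first dose of IMP only", and footnote 6 to Protocol Appendix 1 says the same. Protocol 9.1.1.2 opens its Visit 2 list with "The following will be collected/assessed prior to the patient receiving IMP". ECG is not on that list; it comes later in the section, tied to the same post-dose window. For Visits 3 and 4, footnote 7 has the ECG "to be performed both prior to the day's first dose of IMP and between 3 and 5 hours after this dose".

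SAP 4.8.5 summarizes ECG at screening, at baseline and at each treatment time point, and gives no ECG-specific baseline. Table 14.3.2 in SAP 6.1 reports ECG change from baseline by visit. SAP 4.2.10 adds that "Any clinical domains that are displayed by visit will be shown by nominal study visit".

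**The concern.** The fallback equates being done as planned with being done before dosing. For the Day 1 ECG the plan is the opposite, so a programmer holding an untimed Day 1 ECG cannot satisfy both halves of the clause:

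- Following the plan, the ECG is post-dose and the screening ECG stays as baseline.
- Following the explanatory half, the Day 1 ECG is pre-dose, is the most recent such record, and replaces the screening ECG.

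On the second route a value recorded on drug becomes the reference for that patient's later ECGs. Any change already present 3 to 5 hours after the first dose disappears from the change-from-baseline summary. ECG is named in the primary safety endpoint of both phases (SAP 2.5), so the reference should be unambiguous.

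**Working it through.** There is no stated figure in the plan to reproduce. The check compares the rule with the schedule and then traces the arithmetic.

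**1. Planned ECG times** (SAP Table 1 with footnotes 6 and 7; Protocol 9.1.1.1 to 9.1.1.5)

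| Visit | Planned ECGs | Timing |
|---|---|---|
| 1 (screening) | 1 | before treatment |
| 2 (Day 1) | 1 | 3 to 5 h post-dose only |
| 3 and 4 | 2 each | pre-dose and 3 to 5 h post-dose |
| 5 to 12 | 1 each | no time relative to dose in the table |
| End of taper | 1 | no time relative to dose in the table |

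The only scheduled ECG before the first dose is at Visit 1. Because Visits 3 and 4 ask for a pre-dose ECG explicitly, its absence at Visit 2 is part of the plan.

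**2. Other assessments at Visit 2.** Vital signs, physical examination and Vineland-II are on the pre-dose list in Protocol 9.1.1.2, so the fallback fits them. Laboratory samples are not scheduled at Visit 2, and PK sampling is confined to pivotal-phase patients (SAP Table 1, footnote 8). In the pilot phase, ECG is the only Visit 2 assessment for which the fallback points the wrong way.

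**3. Effect on one patient.** Let B be the screening value, B + d the Day 1 post-dose value and X any later value.

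- Visit 2: the correct change is (B + d) − B = d; the reported change is (B + d) − (B + d) = 0.
- Later: the correct change is X − B; the reported change is X − (B + d) = (X − B) − d.

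Scheduled ECGs after Visit 2 that carry the shift:

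- OLE and taper completed: 2 + 2 + 8 + 1 = 13.
- Pilot completed, OLE declined, taper completed: 2 + 2 + 1 = 5.

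**4. Effect on a visit mean.** One affected patient among n contributing patients moves the mean by |d|/n. SAP 4.1 gives n = 9. No document gives d, so these QTcB values are assumptions:

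| Assumed d, absolute (msec) | Shift of the mean at n = 9 (msec) |
|---|---|
| 5 | 5/9 = 0.56 |
| 10 | 10/9 = 1.11 |
| 20 | 20/9 = 2.22 |

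With no untimed Day 1 ECG, or with the schedule followed, the shift is 0.

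**The case against.** The strongest defence is that the operative instruction is to assume the plan was followed. The SAP's own plan for this ECG is post-dose only, so a careful programmer keeps the screening ECG, and the explanatory half is a loose gloss that suits the other assessments. That reading is available and does no harm. It does not remove the conflict, because the pre-dose half is written as the meaning of the rule and SAP 4.8.5 offers no exception.

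The second defence is that two things must go wrong together: a missing time and the adverse reading. That stands. Protocol 9.2.8 and SAP 4.8.5 require the ECG to be annotated, signed and dated and do not mention a clock time. A reader might infer that times are commonly missing, but the CRF is not among the documents and may well capture them.

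The third is that little depends on the result. That also stands. No hypothesis is tested (SAP 4.2.1). SAP 4.8.5 lists every ECG value and summarizes screening separately. ECG change from baseline appears only in the title of Table 14.3.2, not in the text of SAP 4.8.5 or Protocol 13.6.5.4.

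Two stronger readings are tempting and should be resisted:

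- A reader might infer that the ECG baseline is post-dose throughout. The main rule of 4.2.9 is sound and gives the screening ECG; only the fallback misfires.
- A reader might infer that the QTcB withdrawal criterion, which uses a shift from baseline, would be distorted. The documents do not link that criterion to this SAP derivation.

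**Conclusion.** The text conflict is certain: for ECG, the fallback in SAP 4.2.9 cannot be reconciled with the SAP's own schedule or with the protocol. Whether it affects any result is unknown. An effect needs at least one Day 1 ECG without a recorded time and a programmer who follows the pre-dose wording. In that case each affected patient loses the Visit 2 change and carries an error of minus d in up to 13 later scheduled ECGs. The msec figures rest on assumed values of d and are illustrative. The consequence stays within descriptive ECG change-from-baseline summaries. Severity is minor; high confidence applies to the conflict in the text, not to the size of any effect.

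**What to change.** Add one sentence to SAP 4.2.9:

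> This assumption does not apply to ECG; a Visit 2 ECG with no recorded time is treated as post-dose.

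Nothing more is needed, because the main rule then governs: ECG baseline is the last ECG before the first dose, which as scheduled is the screening ECG. It also deals with unscheduled recordings, which the protocol permits ("Additional ECG measurements can be taken at any time during the trial, if clinically indicated"). An extra ECG dated before Day 1 qualifies on its date alone, and one taken on Day 1 qualifies if its recorded time precedes the first dose.

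The cost is one SAP sentence. No new data, procedure, output or threshold is required.
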